5.2 Interim Analysis for Day-90 Updates

The CS3 safety results for 90-day safety update are based on the data as of the data cutoff date of 15-Sep-2017. Immunogenicity results are based on a data cutoff date of 08-Jul-2017 due to timing of sample collection, batch sizes, and processing schedules. The following data were included in the interim analyses: dispositions, demographics, concomitant medications, exposure, adverse events (AEs), laboratory results, vital signs, physical examinations, electrocardiograms (ECGs), electroretinograms (ERGs), and immunogenicity {IM).

The following will not be performed as part of this interim analysis:

• Summaries using PPS, FAS, ECHO subgroup, OLEECHO set and Longitudinal analysis set

- The review of protocol deviations to identify those leading to exclusion from the PPS
- · Descriptive summary for efficacy and PD endpoints

In addition, listings will be provided for patients who will be found with following conditions after Feb. 28th 2017. A note: Feb. 28th 2017 is the data cut for supporting CS2 EOT submission:

- Platelet count <100 X 10"9/L;
- Platelet count confirmed value <100 X 10"9/L;
- Confirmed Nadir Creatinine Clearance by CKD-EPI (ml/min/1.73m2) shift from ISIS 420915
 Baseline to category 2 or above;
- Confirmed nadir creatinine clearance by CKD-EPI decreasing 25% from ISIS 420915 Baseline or more in which percent change= (post-baseline baseline)/baseline;
- Confirmed nadir creatinine clearance by CKD-EPI decreasing 50% from ISIS 420915 Baseline or more in which percent change= (post-baseline - baseline)/baseline.

The table below lists what data will be included in the summary output by endpoint type and what output isplanned for this interim analysis for Day-90 updates.

Provided at interim of OLE study (Day-90 updates)	Comment
Patient Characteristics	
 Summaries of patient disposition, protocol deviations, analysis sets. 	- For all enrolled patients
 Summary of demographic characteristics and baseline characteristics (excluding efficiacy endpoints) and exposure to Study Drug. 	- For SS
Concomitant medication.	- On-study summary for SS
Corresponding listings.	
Safety Endpoint	
• Summary tables for AE.	- On-Study for SS
• Summary tables of safety lab, vital sign, ECG, ERG by visit.	- On-Treatment+ Post-Treatment for SS
• Summary table and shift table of abnormal safety lab results, ECG worst values and stopping rules.	- Abnormal safety lab is on-study for SS
Corresponding listings.	- All results collected in CS3 before IA data cut
Immunogenicity	
 Summary table for sample IM status, anti-ISIS 420915 antibody titer values, patient IM status, onset and peak titer of the ADA, time to reach peak titer. Box Plot of Titer over Time. 	- On-study summary for SS

Provided at interim of OLE study (Day-90 updates)	Comment
Summary table of AE by patient IM status.	AE is On-Study for SSPatient IM status ison-study for SS
Summary table and shift table of abnormal safety lab results by patient IM status.	 Abnormal safety lab is on-study for SS Patient IM status ison-study for SS
Corresponding listings.	- All results collected in CS3 before IA data cut
PK	
Summary table of (SIS 420915 Trough Plasma Concentrations (ng/ml) with and without Stratification by Subject Immunogenicity Status	- On-study for PK set
Figure of Mean (±SD) of (SIS 420915 Plasma Trough Concentrations (ng/ml) over Time Subject Immunogenicity Status	 On-study for PK set plot time points where at least 20% of the CS3 population have data
Corresponding listings	- All results collected in CS3 before IA data cut

5.3 Interim Analysis II

CS3 Initerim analysis II are based on the data as of the data cutoff date of 31-MAY-2018. The following data were included in the interim analyses: dispositions, demographics, concomitant medications, exposure, adverse events (AEs), laboratory results, ECHO, mNIS+7, NIS, NIS-LL, Norfolk SF36, and PND score.

The table below lists what data will be included in the summary output by endpoint type and what output is planned for this interim analysis II.

Provided at interim II	Comment
Patient Characteristics (for CS3 and ISS)	
 Summary of demographic characteristics and baseline characteristics (excluding efficiacy endpoints) and exposure to Study Drug. 	- For SS
Concomitant medication.	- On-study summary for SS
Listings for exposure, dropouts and dose pause	

Provided at interim II	Comment
Safety Endpoint (for CS3 and ISS)	
Summary tables for AE.	- On-Study for SS
Summary tables of safety lab (Hematology, Chemistry) by visit.	- On-Treatment+ Post-Treatment for SS
 Summary table and shift table of abnormal safety lab results and stopping rules. 	- Abnormal safety lab is on-study for SS
Survival plot for time from first ISIS dose to death or discontinuation	- On-Study for SS
 Listing of adverse events and medication occurred or took 30 days prior to platelet value <50x10⁹/L 	
 Listing of platelet values and anticoagulants or antiplatelets medication for subjects with grade 3 thrombocytopenia 	
Efficacy (for CS3)	
Summary table of mNIS+7, NIS, NIS-LL, SF-36 and PND score, NT-proBNP and Log-Transformed NT- proBNP	- On-treatment for FAS
Listing of NSC domain, subdomain and totalscore	- CS3 Enrolled Patients
PD Parameters (for CS3)	
Summary of TTR and RBP4 by visit.	- On-treatment for FAS
ECHO (for CS3)	
Global Longitudinal Strain and Global Left Ventricular Size and Function - LV Mass	- On-treatment for Enrolled Patients and CM-ECHO Set

Interim II also create Topline efficacy/safety tables by subgroup/subset for CS3 (both efficacy and safety outputs) and ISS (safety outputs). The subgroup/subset are:

- Stage 3 patients (PND score=V at BL)
- V30M TTR Mutation (IVRS)
- Disease Stage (IVRS)
- Previous Treatment (IVRS)
- CM-ECHO Set

- NT-proBNP>650 pg/nL at BL
- NYHA 1 vs 2 at BL
- IVS>15 mm at BL
- Paitents who Diagnosed as TTR Cardiomyopathy at BL
- Efficacy of patients who had pauses vs those who didn't
- Patients who had pauses vs those who didn't (for primary endpoints only)
- Patients on lower dose which is subjects with dose <=150 for more than 12 weeks in CS2 and CS3 (for primary endpoints only)

6. Study Conduct to Minimize Bias

The sponsor recognizes the importance of confidentiality of interim results before the parent study is unblinded. To minimize any potential risk to the integrity of the study, the first interim analysis will be conducted only after the database of the parent study is locked and unblinded.

The ISIS 420915 CS2/CS3 DSMB will conduct regular safety reviews throughout the study. Until the parent study is unblinded, the outputs will be prepared by an independent statistician who is independent from the sponsor.

The independent statistician who supports DSMB will be an employee of a CRO (InVentiv), one that is independent from a second CRO conducting the trial (ICON) and a third CRO (PAREXEL) who will be performing the final statistical analysis. InVentiv will also provide programming support for the DSMB, handle all DSMB related analyses, independent of the Sponsor and independent of ICON and PAREXEL. The independent statistician from InVentiv will maintain secure custody of blinded and unblinded data to ensure the integrity of the data. Additionally, the independent statistician will maintain all unblinded data in electronic form in a secure area. All transfer of data/reports by the independent statistician to the DSMB, which includes patient data will be by secure, trackable courier and/or secure electronic means. The independent statistician will provide all of the unblinded data to the DSMB as outlined in the DSMB Charter.

All DSMB members will sign a Confidentiality Agreement with the Sponsor. In addition, all DSMB members will treat as confidential the reports, meeting discussions, minutes and recommendations of the DSMB. Strict rules for DSMB communication with the Sponsor have been put in place for the purpose of minimizing the potential for bias, as outlined in the DSMB Charter. All written communication described in the DSMB Charter will be by secure, trackable courier and/or secure electronic means. This includes dissemination of DSMB recommendations, and review of minutes of open and closed sessions between the DSMB and, as appropriate, other DSMB members and/or, the Sponsor contacts (primary, CMO and statistics).

During the conduct of this OLE study and before unblinding of the parent study, the Sponsor will not have access to any efficacy, PD or exploratory data, except for parent study baseline values and data collected after the Week 13 visit for the following endpoints: plasma retinol, plasma TTR, plasma RBP4 and plasma NT-proBNP. The efficacy data will be collected and stored by independent CROs as detailed below. All CROs will maintain secure custody of their databases. The CROs will not transfer any efficacy data other than baseline data or post-Week 13 data for certain endpoints to the Sponsor until after all patients in the parent study have completed the treatment period and the database of the parent study has been locked and unblinded. The efficacy or PD data includes the following: mNIS+7, NIS+7, Norfolk QOL-DN, BMI/mBMI, plasma retinol, plasma retinyl palmitate, plasma TTR, plasma RBP4, plasma NT-proBNP, SF-36 questionnaire, ECHO efficacy parameters, NSC and PND scores. Derived mNIS+7 and the components including NIS, +7 and modified +7, as well as NSC, Norfolk QOL-DN, PND, body weight and ECHO will be available before the parent study is unblinded to PAREXEL who are preparing this SAP and are performing statistical analysis.

For the purpose of data cleaning, an independent data manager at Trennic Data Services will also have access to post-baseline data for the following endpoints: mNIS+7, NIS+7, Norfolk QOL-DN, BMI/mBMI, SF-36 questionnaire, ECHO efficacy parameters, NSC and PND scores.

The Norfolk QOL-DN, body weight (needed to calculate BMI/mBMI), SF-36 questionnaire and PND scores will be entered into the EDC system by each site. The independent CRO BioClinica is contracted to develop and maintain secure custody of the EDC database. During the conduct of this OLE study before unblinding of the parent study the Sponsor will receive regular data transfers from BioClinica but without the above mentioned efficacy data included (except for baseline values). Post-baseline values for most endpoints mentioned above except for SF-36 derived scores will be available for PAREXEL who are preparing this SAP and are performing statistical analysis.

The plasma retinol, plasma TTR, plasma RBP4, and plasma NT-proBNP samples will be assayed at Medpace, the central laboratory contracted for this study. The results will be maintained in Medpace's secure database. Neither the Sponsor nor the sites will receive the results from the above mentioned tests (except for baseline values) prior to week 13. During the conduct of this OLE study before unblinding of the parent study the Sponsor will receive regular lab data transfers from Medpace to perform safety assessments. The above mentioned data collected prior to Week 13 will not be available to PAREXEL or the sponsor.

The ECHO data will be collected, analyzed and stored in a secure database by CICL. The sites will upload the ECHO data on a secure web-portal for analysis by CICL. Up until the parent study database lock, the Sponsor will only have access to patient baseline ECHO values. ECHOs conducted for safety assessment purposes will be available to the DSMB, Sponsor, and Investigator. Post-baseline ECHO data will be available for PAREXEL who are preparing this SAP and are performing statistical analysis.

Prior to the parent study unblinding, any ISIS 420915 concentration data sets and IM data sets provided to Ionis Pharmaceuticals, Inc. by the respective bioanalytical labs will not include results for samples collected prior to Week 13, nor will they include results for unscheduled or early term (ET) samples to prevent the potential unblinding of the parent study.

In conclusion, the unblinding process before the parent study unblinding for periodic safety reviews has been clearly defined and detailed roles and responsibilities to the independent statistician, DSMB, Partner Firewalled Staff and Sponsor, such that the potential for bias to enter into the conduct of the study will be minimized. Additional steps to ensure the data for the primary and secondary endpoints remain blinded, such as housing the primary and secondary efficacy data in databases to which the Sponsor has no access, further safeguards the potential for Sponsor bias.

7. References

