8.5.4 Safety Monitoring Rules for Platelet Count Results

Platelets will be monitored weekly throughout the treatment period and for a minimum of 6 weeks after the last dose of Study Drug (this includes early termination patients as well as patients that complete the full treatment period). For patients participating in the Post-Treatment Evaluation Period, frequency of testing after 6 weeks from the last dose of Study Drug will be determined by the Investigator in consultation with the Study Medical Monitor.

All platelet count results must be promptly reviewed by the Investigator to ensure that the count has not met the stopping rule

If for any reason there is more than 14 days between platelet values (e.g. lab report of an unreadable sample due to clumping, hemolysis, or quantity not sufficient, or a missed lab assessment), the Investigator will contact the patient to hold dosing until a new platelet value is obtained and reviewed.

If a patient's platelet counts fall below 100,000/mm³, additional lab tests may be requested as determined by the Investigator in consultation with the Study Medical Monitor.

Due to the 3 to 5-year study duration it is anticipated that patients may undertake travel including vacations, which may impede weekly platelet monitoring. In some situations it may be possible to arrange for local laboratory testing or use of the home healthcare service at their temporary location. The intent is to maintain weekly platelet monitoring and dosing where possible, as well as Investigator site contact with the study patients. However, if the above options are not possible, a temporary interruption of study treatment will be planned with a prompt blood draw upon the patient's return which must be reported and reviewed by the Investigator prior to the patient resuming dosing.

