8.6.3 Stopping Rule for Platelet Count Results

In the event of a confirmed platelet count less than 75,000/mm³, and in the presence of major bleeding or clinically-relevant non-major bleeding (defined below; Schulman et al. 2005), dosing of a patient with ISIS 420915 will be stopped permanently. The follow-up schedule for any

^{*} baseline is study CS3 Day 1 value

events meeting this stopping criterion will be determined by the Investigator in consultation with the Study Medical Monitor.

In the event of a confirmed platelet count less than $75,000/\text{mm}^3$, and in the absence of major bleeding or clinically-relevant non-major bleeding, further dosing of a patient with ISIS 420915 must be held until the platelet count returns to at least $100,000/\text{mm}^3$. Weekly platelet monitoring should continue during this period. In addition, the Investigator should give consideration to collecting duplicate platelet samples for study in a local lab in parallel to the central lab if it would provide quicker access to the patients platelet count. If the platelet count was confirmed to be $< 50,000/\text{mm}^3$, then monitoring should be increased to daily until two successive values show improvement. The Investigator must notify the Study Medical Monitor within 24 hours of any local lab platelet results that show a level $< 50,000/\text{mm}^3$.

The suitability of the patient for continued dosing and the need for any modification to treatment schedule or dose (refer to Section 8.7) will be determined by the Investigator in consultation with the Study Medical Monitor and will be based on factors such as the original rate of decline in the patient's platelet count, whether any bleeding events were experienced by the patient, and the speed of recovery of platelet count upon holding of dosing.

Definition of major bleeding events:

International Society on Thrombosis and Haemostasis (ISTH) Major Bleeding:

- 1. Fatal bleeding, and/or
- 2. Symptomatic bleeding in a critical area or organ, such as intracranial, intraspinal, intraocular, retroperitoneal, intraarticular or pericardial, or intramuscular with compartment syndrome, and/or
- 3. Bleeding causing a fall in hemoglobin level of 20 g/L (1.24 mmol/L) or more within 24 hours, or leading to transfusion of 2 or more units of whole blood or red cells

Definition of clinically-relevant, non-major bleeding events:

- 1. Multiple-source bleeding
- 2. Spontaneous hematoma $> 25 \text{ cm}^2$

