3.2.1.4 Data Summary Plan

The table below details what data will be included in the summary and analysis output by endpoint type. Data summarized or analyzed at each interim analysis will be based on data collected up to the data cut date. It is possible that on-treatment data and post-treatment data available for each interim analysis is different from the final analysis at the end of study because data collected after each interim analysis data cut may slot into different treatment period. Outputs will be updated for each interim analysis and for the final analysis. In select instances the data for a type of endpoint that is summarized or analyzed may not be consistent with the rules in the table below; such exceptions will be noted in this document.

Endpoint type	Output type	Comment/definition
Efficacy	-Listings -On-treatment (CS2&CS3) summary/analysis tables -Post-treatment summary tables	-On-treatment (CS2 period):The CS2 Study Day 1 S Date of assessment S Last dose date in parent study+ 52 days -On-treatment (CS3 period): CS3 STUDY DAY 1 \$ Date of assessment S Last dose date of OLE study+ 52 days -showing both CS2 visits and CS3 visits. Note the results of the analyses at the CS2 visits will not be the same as the results from the CS2 study as this table only includes patients in the CS3 FASPost-treatment: Date of assessment > last dose date of OLE study + 52 days -Visit defined by analysis visit window
PD, BMIand mBMI	-Listings -On-treatment (CS2&CS3) summary/analysis tables -Post-treatment summary tables	-On-treatment (CS2 period): The CS2 Study Day 1 S Date of assessment S Last dose date in parent study+ 28days -On-treatment (CS3 period): CS3 STUDY DAY 1 S Date of assessment S Last dose date of OLE study+ 28days -showing both CS2 visits and CS3 visits. Note the results of the analyses at the CS2 visits will not be the same as the results from the CS2 study as this table only includes patients in the CS3 FAS.

Endpoint type	Output type	Comment/definition
		-Post-treatment: Date of assessment> last dose date+ 28days -Visit defined by analysis visit window
Safety Endpoints: ECG, Lab, vitals sign (including body weight)	-Listings -On-treatment summary tables (CS3) -Post-treatment summary tables	-On-treatment (CS3 period): CS3 Study Day Is Date of assessment 5 Last dose date + 7 days -Post-treatment: Date of assessment> last dose date+ 7 days -Visit defined by analysis visit window

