Missing/partial dates (month and year) for the duration of disease from diagnosis for FAP/FAC and duration from onset of symptoms for FAP/FAC will be imputed as follows: since CRF only collects year and month for FAP and FAC Diagnosis and onset of symptoms, for calculating the duration, a day of 15th will be used if only day is missing. JUL01 will be used if both day and month are missing. If the imputed date is after the date of informed consented at CS2, use the informed consented at CS2 as the imputed date. Calculate as following

- (a) Duration (month) = number of month (date of informed consented at CS3- date of FAP or FAC diagnosis + 1)
- (b) Duration (month) = number of month (date of informed consented at CS3- date of onset of FAP or FAC symptoms + 1)

Exposure to Study Drug in OLE study will be summarized by treatment group of the parent study for the SS by durations of drug exposure in OLE study (days), total number of dose received, and total dose administered (in milligrams). Across all visits, number of subjects with dose pauses and reasons for dose pause will be tabulated. A listing presenting for each subject the number of dose reductions (frequency of administered dose < protocol defined dose, i.e. 300 mg) and missed doses (injection not givens) will be provided. Doses that were not given because the patient discontinued will not be summarized.

Overall drug exposure from the start of the parent study to the end of the OLE study will be summarized for patients who took ISIS 420915 in the parent study, i.e. LSS.

Medical history and baseline physical examination findings collected in the OLE study will be listed depending on the data availability.

Medications will be coded using WHO Drug Dictionary. The final version used will be designated in the clinical study report. Concomitant medications used will be summarized by treatment group for the SS and the CM-ECHO Set.

All medications including concomitant medications will also be listed in a by patient listing. In the listing, medications which are started before the **CS3 Study Day 1** will be marked.

Patients with any anti-platelet or anti-coagulant medication taken at any time during this study will be presented in a listing.

A concomitant medication is defined as any medication taken whilst investigational product is being taken in this study.

If a partial date is recorded in the case report form, the following convention will be used to assign the medication:

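### The Interim Analysis II pause subset (SAP 5.3) neither defines a pause nor says when it must occur, so pauses after an efficacy visit could decide the group at that visit

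*Combined protocol and SAP*

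**What the plan says.** SAP 5.3 asks for topline tables by subgroup or subset at Interim Analysis II. One entry is "Efficacy of patients who had pauses vs those who" did not. The next repeats the contrast, "patients who had pauses vs those who" did not, for the primary endpoints. Efficacy at this interim is the on-treatment summary on the Full Analysis Set, and SAP 3.4 performs efficacy summaries by analysis visit.

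On the period covered, SAP 5.3 states: "CS3 Initerim analysis II are based on the data as of the data cutoff date of 31-MAY-2018". The general rule in SAP 3.2.1.4 is: "Data summarized or analyzed at each interim analysis will be based on data collected up to the data cut date".

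The main other place where the SAP tabulates pauses is the exposure summary in SAP 3.2.3: "Across all visits, number of subjects with dose pauses and reasons for dose pause will be tabulated". The same section adds: "Doses that were not given because the patient discontinued will not be summarized".

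The protocol gives several routes to an interruption:
- Section 8.6.3: after a confirmed platelet count below 75,000/mm³ without relevant bleeding, dosing "must be held until the platelet count returns to at least" 100,000/mm³.
- Section 8.5.4: a hold applies "If for any reason there is more than 14 days between platelet values", and interruptions for travel are foreseen.
- Section 8.5: no re-dosing while a result that meets a stopping criterion awaits confirmation.
- Sections 8.5.2 and 8.7: pauses for renal findings and for adverse events.

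The neighbouring entries in SAP 5.3 are mostly fixed at baseline or randomization. The low-dose subset is also post-baseline, but it states a dose threshold, a duration and the studies covered (CS2 and CS3). The pause entries state none of these.

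**The concern.** A pause happens after baseline, and its chance of having happened grows with time on drug. When such an event defines the columns of a by-visit table, the plan must say up to what time it is looked for. Without that rule, a patient whose first pause comes at Week 100 would have the Week 26 and Week 52 scores reported under paused, although dosing was uninterrupted at both visits. A patient who stops treatment early has had less time to pause and so drifts towards the no-pause column. This is the familiar immortal-time problem.

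A reader would naturally use the table to judge whether interrupting treatment costs efficacy. If much of the paused column has not yet paused, a real loss is diluted. If early stopping is also linked to progression, the no-pause column collects faster progressors and the paused group can look better for no good reason. Both errors lean towards false reassurance.

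**Working it through.** **What is given and what is assumed.** The documents state no pause rate, sample size or power for this contrast, so there is no figure to reproduce. From the documents: parent-study randomization 2:1, 65 weeks of parent-study treatment, and efficacy visits at Weeks 26, 52, 78 and 104. Assumed: a constant weekly chance h of a first pause of 0.25%, 0.5% or 1%; 104 CS3 weeks at the cut for everyone; no discontinuation; and, where CS2 counts, that the 2:1 ratio carries into CS3.

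**Only CS3 pauses count.** With q = 1 − h:
- ever paused by Week 104 = 1 − q^104
- share of the paused group not yet paused at Week v = 1 − (1 − q^v)/(1 − q^104)

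For h = 0.005: ever paused = 40.6%; paused by Week 26 = 12.2%; share not yet paused = 1 − 0.122/0.406 = 70%.

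**CS2 pauses also count.** Two-thirds of patients bring 65 earlier weeks, so their clock runs to 65 + 104 = 169 weeks:
- ever paused = (2/3)(1 − q^169) + (1/3)(1 − q^104)
- first pause after Week v = (2/3)(q^(65+v) − q^169) + (1/3)(q^v − q^104)

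For h = 0.005, v = 26: (2/3)(0.205) + (1/3)(0.284) = 0.231. Ever paused = (2/3)(0.571) + (1/3)(0.406) = 0.516. The ratio is 45%.

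| Weekly chance h | Ever paused, CS3 only | Not yet paused W26 / W52, CS3 only | Not yet paused W26 / W52, CS2 and CS3 |
|---|---|---|---|
| 0.25% | 23% | 73% / 47% | 49% / 31% |
| 0.5% | 41% | 70% / 44% | 45% / 28% |
| 1% | 65% | 65% / 37% | 37% / 22% |

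A wider grid for CS3 pauses only (10% to 50% paused by Week 52, follow-up 78 to 156 weeks, exponential first-pause time) gives 55% to 81% at Week 26 and 23% to 63% at Week 52.

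**Dilution.** If a pause had an immediate and constant effect, the Week 26 contrast would show one minus the not-yet-paused share: about 27% to 35% of the true effect (CS3 only) or 51% to 63% (CS2 and CS3).

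**Early stoppers.** With 10% to 50% paused by Week 52, a patient who stops at Week 26 has a 5% to 29% chance of a pause label, against 19% to 75% for a patient treated for 104 weeks.

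**Null simulation.** 400,000 patients, pauses without any effect and CS3 pauses only; 15% stop by Week 52 at average risk; 30% or 50% have a first pause by Week 52; 104 weeks of follow-up; assessments kept up to 52 days after the last dose. With a label fixed at the cut-off:
- When stopping is linked to progression (log hazard ratio 0.4 to 1.0 per SD), the false difference in favour of the paused group is 0.06 to 0.16 SD at Week 26, 0.03 to 0.07 SD at Week 52, and about 0.02 SD or less from Week 78.
- When stopping is unrelated to progression, the difference is about zero.
- About 56% to 74% of early stoppers are labelled no pause.

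With a label based only on pauses before each visit, the difference is within 0.01 SD at every visit.

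**The case against.** The strongest reply is that SAP 5.3 leaves the label open and does not prescribe a wrong one. That stands. A reader might infer that the plan lays down a single ever/never label to the cut-off, but no such wording appears. It is the natural reading only because the contrast is per patient, the data run to the cut, and SAP 3.2.3 counts subjects across all visits; that last sentence concerns the exposure summary, not this subset.

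A reader might also infer that early stoppers are counted as no pause. No rule says so. Protocol 9.4.3.3 separates interruption with restart from permanent discontinuation, so a patient who stops with no earlier pause would fall there by default. For laboratory toxicity, though, a hold often precedes stopping (Protocol 8.5, 8.5.2 and 8.6.3), and the SAP does not say whether such holds are pauses.

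A third tempting reading is that early visits mostly compare patients who have not yet paused with patients who never pause. That holds under these assumptions only if CS2 pauses are ignored. If they count, the share at Week 26 is below half.

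Finally, SAP 3.2.1.3 excludes efficacy assessments more than 52 days after the last dose, so early stoppers do not remain in the no-pause column at later visits. The tables are descriptive and SAP 1.3 states no formal hypotheses. These points limit the size and reach of the problem. They do not supply the missing time rule.

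**Conclusion.** The concern holds as a gap in definition and timing. A post-baseline, exposure-dependent grouping is applied to by-visit efficacy tables without a definition of a pause, the studies covered, or its timing relative to the visit. On the plain reading, later pauses would decide the group at earlier visits, and stoppers with no earlier pause would be in the no-pause group.

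The size cannot be known from the documents. The ranges above rest on assumed pause and stopping rates, and the answer depends heavily on whether CS2 pauses count, which the SAP leaves open. The false difference of up to 0.16 SD also needs stopping to be linked to progression. Distortion is greatest at Weeks 26 and 52; the documents do not support a claim of serious bias at later visits.

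The effect is confined to Interim Analysis II, a descriptive analysis with a 2018 cut-off that SAP 5.3 partly describes in the past tense. Since SAP 9.1 removes efficacy by subgroup from the final analysis, the final plan has no subgroup table that would correct a misleading contrast.

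**What to change.** In SAP 5.3:
1. Define a dose pause for analysis: minimum length, qualifying reasons, CS2 and/or CS3, and whether holds pending a confirmatory result or for travel count.
2. Classify each patient separately at each efficacy visit, using only pauses begun on or before that assessment.
3. State how patients who discontinue treatment are grouped.
4. Show the percentage of scheduled doses received up to that visit alongside.
5. Label the tables descriptive. If they already exist, rerun them or add a footnote stating the limitation.

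The cost is SAP wording and modest programming from the dosing eCRF; SAP 5.3 already calls for listings of exposure and dose pause. The downside is that group sizes change between visits and the paused group is small early on. The rule removes the timing problem only: patients who pause may still differ from those who do not, so the contrast should not be read as the effect of pausing.
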